#### 4.9.1 Definitions

#### **Dose Limiting Toxicity**

See the definition stated under "Definition of DLT" in Section 6.1.1 of Protocol HALO-107-101 Amendment 4 entitled "A Phase 1b Open-Label Study of PEGylated Recombinant Human Hyaluronidase (PEGPH20) Combined with Pembrolizumab in Subjects with Selected Hyaluronan-High Solid Tumors" and dated 6 November 2017.

#### Treatment emergent adverse event

Treatment emergent adverse event (TEAE) is defined as any adverse event with an onset date on or after the first dose of any study drug up through and including 30 days after the last dose of any study drug.

In addition, any adverse event deemed related (i.e., eCRF categories: related, probably related or possibly related) to any study medication by the Investigator will also be considered as TEAE irrespective of the onset date.

#### 4.9.2 Extent of Exposure

Extent of exposure will be summarized for treatment duration, number of cycles initiated, number of doses administered, dose reductions, dose delay, cumulative dose, weight adjusted

cumulative dose, average dose intensity, and relative dose intensity by cancer type and in total separately for the Dose Escalation portion and the Dose Expansion portion.

An overall summary of drug exposure will be presented for the number of cycles initiated with any study medication and duration of treatment for all study medications. Duration of treatment is defined as the time from first dose date of any study medication to the last dose date of any study medication. Overall drug exposure will be summarized using descriptive statistics. The frequency count and percentages will also be presented for subjects who had number of treatment cycles initiated  $>0, \geq 2, \geq 4$ , etc.

For each study medication (PEGPH20 and pembrolizumab), exposure will be summarized using descriptive statistics by cancer type and in total for the following parameters across all cycles.

- Number of cycles initiated
- Duration of treatment
- Number of doses administered
- Frequency and percentage of subjects with at least one dose omitted

For subjects with at least one dose omitted:

- Total number of expected doses up to the last dose received, including doses omitted
- Frequency and percentage of doses omitted
- Frequency and percentage of dose omission by reason, including PEGPH20 toxicity, chemotherapy toxicity, other adverse event, scheduling conflict, discontinued PEGPH20 and other
- Frequency and percentage of subjects with at least one dose PEGPH20 reduction

For subjects with at least one PEGPH20 dose reduction:

- Total number of doses administered
- Frequency and percentage of doses with dose reduction
- Frequency and percentage of subjects with at least one dose delay. A treatment cycle is considered delayed if the first dose date of the following cycle is greater than 28 days after the first dose date of the cycle of interest.

For subjects with at least one dose cycle delay:

- Total number of cycles initiated
- Frequency and percentage of cycles with dose delay
- Frequency and percentage of subjects with at least one dose interruption

For subjects with at least one dose interruption:

- Total number of doses administrated
- Frequency and percentage of doses with dose interruption

- Frequency and percentage of dose interruption by reason, including adverse event and other
- Frequency and percentage of interrupted doses restarted
- Actual dose intensity (ADI) per cycle is defined as the cumulative dose divided by number of adjusted treatment cycles.
  - The weight-adjusted cumulative dose administered for PEGPH20 (in both Dose Escalation and Dose Expansion portions) and pembrolizumab (in the Dose Escalation portion only) is the sum of the respective doses administered at a given visit, divided by the subject's weight measurement (kg) at Screening. Cumulative dose for pembrolizumab (in the Dose Expansion portion only) is defined as the sum of administered doses.
  - If the last dosed cycle is Cycle 1, then number of adjusted treatment cycles is considered to be 1. If the last dosed cycle is Cycle 2 or beyond, then the number of adjusted treatment cycles will be calculated as [(End date of last cycle First dose date + 1) / 21], where the end date of last cycle is calculated as [First dose date of last cycle + (Number of doses received or omitted in the last cycle up to the last dose received) \* 20 / 3] for PEGPH20 and (Dose date + 20) for pembrolizumab. For PEGPH20, if the day of the visit of first dose date of last cycle is not 1, then an adjustment should be made by subtracting 7 or 14 depending on whether the day is 8 or 15 respectively.
- The planned dose intensity (PDI) for PEGPH20 is calculated as follows:
  - For the Dose Escalation portion, if the number of adjusted treatment cycles is 1, then the planned dose intensity per cycle (ug/kg) for each individual dosing cohort will be calculated as [(Dose level in ug/kg) \* Number of doses received or omitted up to the last dose received in Cycle 1]. Else, the planned dose intensity per cycle (ug/kg) for each individual dosing cohort will be calculated as [(Dose level in ug/kg) \* 3].
  - For the Dose Expansion portion, if the number of adjusted treatment cycles is 1, the planned dose intensity per cycle (ug/kg) will be calculated as [(RP2D dose in ug/kg) \* Number of doses received or omitted up to the last dose received in Cycle 1]. Else, the planned dose intensity per cycle (ug/kg) will be calculated as [(RP2D dose in ug/kg) \* 3].
- The PDI for pembrolizumab is calculated as follows:
  - For the Dose Escalation portion, the planned dose intensity per cycle is 2 mg/kg.
  - For the Dose Expansion portion, the planned dose intensity per cycle is 200 mg.
- The Relative dose intensity (RDI) (percent) is defined as follows:
  - [(ADI per cycle) / (PDI per cycle)] \* 100%

In addition to descriptive summary of relative dose intensity, the frequency and percentage of subjects will be presented for the following relative dose intensity

categories:  $\geq$ 90%, 80% to <90%, 70% to <80%, 60% to <70%, 50% to <60%, and <50%.

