7.3. Subject Withdrawal Criteria

7.3.1. Discontinuation of Treatment

The Investigator must guard the subject's welfare and may discontinue study drug treatment at any time when this action appears to be in the subject's best interest. The reason for the subject's withdrawal must be recorded in the subject's electronic case report form (eCRF). Possible reasons for such actions may include, but are not limited to, the following:

- Disease progression (defined in Section 6.1.4).
- AE.
- Any significant protocol violation (e.g., demonstrated lack of treatment compliance, subject starts taking any concomitant anti-cancer therapy).

^{*}Any relevant diseases that are not listed as examples of exclusionary diseases are to be discussed with the Sponsor.

- Withdrawal of consent by an enrolled subject, either for study treatment itself (and subsequent follow-up) or for participation in follow-up.
- Other reasons as determined by the Investigator or Sponsor: a subject may have study treatment discontinued if, in the opinion of the Investigator or Sponsor, it is not in the subject's best interest to continue.
- The subject becomes pregnant (treatment must be discontinued immediately).
- Treatment delay ≥ 21 days.
- Subjects experiencing any TE event that requires full-dose anticoagulation while on study (PEGPH20 will be discontinued; treatment with pembrolizumab may continue as deemed appropriate by the Investigator).
- Gastric adenocarcinoma subjects for whom enoxaparin is discontinued for any reason (PEGPH20 will be discontinued; treatment with pembrolizumab may continue as deemed appropriate by the Investigator).

Subjects who discontinue treatment with PEGPH20 and pembrolizumab should enter long-term follow-up unless they withdraw consent, die, or are lost to follow-up.

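### SAP 4.9.2 measures PEGPH20 dose intensity only up to the last PEGPH20 dose, so an early permanent stop with continued pembrolizumab can still show 97.7% to 100%, and the omission table's denominator does not cover one of its own listed reasons

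*SAP*

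**What the plan says.** SAP 4.9.2 builds the exposure tables drug by drug: "For each study medication (PEGPH20 and pembrolizumab), exposure will be summarized using descriptive statistics by cancer type and in total". For subjects with an omitted dose, the expected-dose line reads "Total number of expected doses up to the last dose received, including doses omitted". Omissions are then broken down by reason, "including PEGPH20 toxicity, chemotherapy toxicity, other adverse event, scheduling conflict, discontinued PEGPH20 and other".

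For dose intensity, "Actual dose intensity (ADI) per cycle is defined as the cumulative dose divided by number of adjusted treatment cycles". If the last dosed cycle is Cycle 2 or later, the PEGPH20 time base ends at a date computed from "Number of doses received or omitted in the last cycle up to the last dose received". Pembrolizumab has its own end date (dose date plus 20 days). If the last dosed cycle is Cycle 1, adjusted cycles are set to 1, and the planned PEGPH20 dose covers only the doses received or omitted up to the last one received. RDI is actual divided by planned intensity, and the top reporting category is 90% or more.

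Protocol 7.3.1 names two situations in which "PEGPH20 will be discontinued; treatment with pembrolizumab may continue as deemed appropriate by the Investigator": a thromboembolic (TE) event that needs full-dose anticoagulation and, in gastric subjects, the end of enoxaparin whatever the reason. The synopsis and Table 6 repeat the TE rule, and the synopsis repeats the enoxaparin rule.

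**The concern.** PEGPH20 is the drug under investigation, and the tolerability of the combination is a secondary objective of Dose Expansion. The protocol foresees subjects who go on with pembrolizumab alone. For them, the RDI window closes at the last PEGPH20 dose, so every PEGPH20 dose not given afterwards drops out of the calculation. A subject with a single PEGPH20 dose and many pembrolizumab cycles can share the top RDI category with a subject who received every dose of both drugs.

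The omission table has a related problem. It plans a row for doses omitted because PEGPH20 was discontinued, but the expected-dose count beside it ends before such doses can arise.

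**Working it through.** The SAP states no numerical dose intensity, so there is no figure to reproduce. The check applies its formulas to subjects dosed on schedule until a permanent PEGPH20 stop.

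**Formulas (SAP 4.9.2), dose level set to 1, first dose on day 1**
- k = doses received or omitted in the last cycle, up to the last dose received.
- End date = first dose date of the last cycle + k × 20/3.
- Adjusted cycles = (end date − first dose date + 1)/21, or 1 if the last dosed cycle is Cycle 1.
- Planned intensity = 3 per cycle, or k if the last dosed cycle is Cycle 1.
- RDI = 100 × (doses given/adjusted cycles)/planned intensity.

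**Stop in Cycle 1 after k doses:** (k/1)/k = 100% for k = 1, 2 or 3.

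**Stop in Cycle 2** (cycle starts on day 22):
- After Day 1: end date 22 + 6.67 = 28.67; adjusted cycles 28.67/21 = 1.365; RDI = (4/1.365)/3 = 97.7%.
- After Day 8: end date 35.33; adjusted cycles 1.683; RDI = (5/1.683)/3 = 99.1%.
- After Day 15: end date 42; adjusted cycles 2; RDI = (6/2)/3 = 100%.

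**Later stops after Day 1, Day 8 or Day 15:** Cycle 3 gives 98.7%, 99.4% and 100%; Cycle 4 gives 99.1%, 99.6% and 100%; Cycle 6 gives 99.4%, 99.7% and 100%. Every case falls in the top category. A subject held from Cycle 2 Day 8 who never resumes also shows 97.7%, because trailing omissions are not counted.

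**The same doses over the whole treatment period.** The number of pembrolizumab cycles is an assumption (4, 8 or 12). The denominator is three PEGPH20 doses per cycle, that is 12, 24 or 36.

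| PEGPH20 stops after | Doses | RDI as written | 4 cycles | 8 cycles | 12 cycles |
|---|---|---|---|---|---|
| Cycle 1 Day 1 | 1 | 100% | 8.3% | 4.2% | 2.8% |
| Cycle 2 Day 1 | 4 | 97.7% | 33.3% | 16.7% | 11.1% |
| Cycle 2 Day 15 | 6 | 100% | 50.0% | 25.0% | 16.7% |
| Cycle 4 Day 15 | 12 | 100% | 100% | 50.0% | 33.3% |

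Counting whole cycles matches the SAP's own end date for pembrolizumab. If counting stopped on the date of the last pembrolizumab dose (Day 1 of the last cycle), the Cycle 2 Day 15 row would use 10, 22 and 34 expected doses: 6/10 = 60%, 6/22 = 27.3% and 6/34 = 17.6%.

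**Omissions before the last dose do lower RDI.** Two doses missed in Cycle 2 with the last dose on Cycle 3 Day 15 gives (7/3)/3 = 77.8%. Cycle 2 Day 1 missed with the last dose on Cycle 2 Day 15 gives (5/2)/3 = 83.3%.

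**Omission table.** Take the stop after Cycle 2 Day 15 with eight pembrolizumab cycles. Expected doses up to the last PEGPH20 dose are 6, and scheduled doses not given afterwards are 24 − 6 = 18. If the window limits the omission count, none of the 18 appears. If it does not, 18 omissions stand against 6 expected doses.

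**The case against.** The strongest reply is that RDI to the last dose is an accepted convention: it describes dosing while on the drug, and discontinuation is a separate quantity. Protocol 11.1.7 asks for relative dose intensity without naming a window, so the SAP contradicts nothing. An RDI over all treatment time also depends on how long pembrolizumab lasts: 12 PEGPH20 doses give 100%, 50% or 33%, so longer time on pembrolizumab looks like poorer PEGPH20 dosing. This stands, and it is why the present RDI should be supplemented and not replaced.

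Other planned tables also help. SAP 4.9.2 gives cycles initiated and doses administered for each drug, so a short PEGPH20 course is visible in aggregate. SAP 4.9.4 tabulates TE events, adverse events leading to discontinuation of study drug, and PEGPH20-related events leading to its discontinuation. None of these relates PEGPH20 exposure to time on pembrolizumab. The PEGPH20-specific table is limited to related events, whereas Table 6 applies the TE rule regardless of relatedness. The only definition given for treatment duration runs to the last dose of any study drug.

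Four stronger readings might be inferred, and the documents do not support them:
- *The omission reason for discontinued PEGPH20 can never occur.* The window is written on the expected-dose line, not on the lines that count omissions or reasons. That line does not say whether the last dose is of that drug or of any drug. The reason list also serves pembrolizumab.
- *Every subject who stops early shows about 100%.* Earlier omissions, delays or reductions lower the figure, as the 77.8% and 83.3% examples show.
- *The subjects placed in the top category are those who tolerated PEGPH20 least.* The mandated stops are not measures of PEGPH20 tolerance: one applies regardless of relatedness and the other follows the end of enoxaparin.
- *About a quarter of subjects would be misclassified.* Protocol 4.5.7.2 reports 4 of 15 (27%) with a TE event in the earlier NSCLC study. That study combined PEGPH20 with docetaxel, and the count includes superficial thrombophlebitis and is not limited to events needing full-dose anticoagulation. The same section gives 10% in the PEGPH20 arm of a pancreatic cancer study after mitigation. Neither figure says how often pembrolizumab continues, or for how long.

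The missing label for pembrolizumab toxicity is a small matter, since the list is open and has rows for other adverse events and other reasons.

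**Conclusion.** The point holds for the dose-intensity formulas and for the fit between the omission reasons and their denominator. For a subject dosed as planned until a permanent PEGPH20 stop, RDI is 97.7% to 100% whenever the stop occurs. The contrast with 50%, 25% or 17% for a stop after Cycle 2 Day 15 rests on assumed pembrolizumab durations and whole-cycle counting. For the RDI, the separate PEGPH20 and pembrolizumab end dates make the window drug-specific. For the expected-dose line, the same window is the natural reading of a per-drug list, but it is not stated.

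The effect is confined to descriptive exposure and tolerability tables. The ORR test is untouched, and the share of subjects affected cannot be derived from the documents. The change is worth making because no planned summary relates PEGPH20 exposure to time on treatment.

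**What to change.** In SAP 4.9.2:
1. Keep the RDI to the last PEGPH20 dose, labelled as dose intensity while on PEGPH20.
2. Add beside it a PEGPH20 RDI with expected doses counted to the last dose of any study drug, stating whether the final pembrolizumab cycle counts in full.
3. Use that same window as the denominator for omitted PEGPH20 doses, so that doses after permanent discontinuation are counted under the reason already listed for it.
4. Tabulate the number of subjects and cycles on pembrolizumab alone.
5. As an editorial correction, replace the chemotherapy-toxicity reason with pembrolizumab toxicity, since the study regimen contains no chemotherapy.

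The cost is SAP wording and a few derived variables from dosing dates already collected. PEGPH20 dose intensity will look less favourable in the added row. That row varies with pembrolizumab duration, so it should be read only beside the existing RDI.

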8.3. Study Drug Administration

Each treatment cycle is 21 days (3 weeks).

In Dose Escalation, PEGPH20 will be administered on Day 1, Day 8 and Day 15 of each 21-day cycle (i.e. 3 doses/cycle) and pembrolizumab (2 mg/kg every 21 days) on Day 1 of each cycle (i.e. 1 dose/cycle), 4-6 hours after the completion of PEGPH20 administration.

In Dose Expansion, PEGPH20 will be administered on Day 1, Day 8 and Day 15 of each 21-day cycle (i.e. 3 doses/cycle) and pembrolizumab (200 mg every 21 days) on Day 1 of each cycle (i.e. 1 dose/cycle), 4-6 hours after the completion of PEGPH20 administration.

Treatment in both portions of the study will continue until disease progression or unacceptable toxicity, death, or withdrawal of consent from the study.

If a dose of PEGPH20 is missed on Day 1 of cycle 2 or beyond, the cycle will continue as scheduled. If it is known that pembrolizumab will be missed or held on Day 1, PEGPH20 should also be held and the cycle will not start until the first dose of pembrolizumab is administered. This will require planning such that the dose of PEGPH20 can be given before the pembrolizumab dose is set to resume.

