	• If toxicity is resolved or reduced to ≤ Grade 2, any PEGPH20 treatment reinitiation must be discussed with the Sponsor's Medical Monitor.		
Thromboembolic Events (Regardless of	ess of Relatedness to PEGPH20)		
Any Grade TE event	Discontinue PEGPH20 treatment for subjects who experience any TE requiring full dose anticoagulation while on study. Treatment with pembrolizumab may continue as deemed appropriate by the Investigator.		

Abbreviations: MSE = musculoskeletal event; NSAIDs = non-steroidal anti-inflammatory drugs; PEGPH20 = PEGylated recombinant human hyaluronidase.

If PEGPH20 is held on Day 1 of treatment cycles 2+, pembrolizumab must still be given.

For details on administration of piroxicam and toradol for the management of MSEs, refer to Section 10.12.1; for information on administration of prophylactic enoxaparin and aspirin for management of TE events, refer to Section 10.12.2 and Section 10.12.3, respectively.

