#### 3.1.2 Phase 1b Dose Expansion Portion

Approximately 51 HA-high subjects will be studied in the Dose Expansion portion at the RP2D identified in the Dose Escalation portion:

- Approximately 30 subjects with Stage IIIB or IV NSCLC, previously untreated or treated and having failed no more than 1 previous platinum-based chemotherapy (refer to Inclusion Criterion #3)
- Approximately 21 subjects with relapsed/refractory gastric adenocarcinoma having failed no more than 2 previous chemotherapy regimens.

In Dose Expansion, PEGPH20 will be administered on Day 1, Day 8, and Day 15 of each 21-day cycle (i.e., 3 doses / cycle) and pembrolizumab (200 mg every 21 days) on Day 1 of each cycle (i.e., 1 dose / cycle), 4-6 hours after the completion of PEGPH20 administration. The dosing schedule is shown in Table 2.

If a dose of PEGPH20 is missed on Day 1 of Cycle 2 or beyond, the cycle will continue as scheduled. If it is known that pembrolizumab will be missed or held on Day 1, PEGPH20 should also be held and the cycle will not start until the first dose of pembrolizumab is administered. This will require planning such that the dose of PEGPH20 can be given before the pembrolizumab dose is set to resume.

Time point	PEGPEM Treatment by Treatment Group		
Subjects with NSCLC			
Cycle 1 and B	eyond (Each Cycle 21 Days)		
Week 1			
Day 1	PEGPH20		
	Pembrolizumab (4-6 hours after PEGPH20)		
Week 2			
Day 8	PEGPH20		
Week 3			
Day 15	PEGPH20		
Subjects with Gastric Adenocarcinoma			
Cycle 1 and B	eyond (Each Cycle 21 Days)		
Week 1			
Day 1	PEGPH20		
	Pembrolizumab (4-6 hours after PEGPH20)		
Week 2			
Day 8	PEGPH20		
Week 3			
Day 15	PEGPH20		

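### SAP 4.9.2 measures cycle delay between first dose dates, so PEGPH20 delay counts can be wrong when a cycle's first PEGPH20 dose falls on Day 8 or Day 15

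*SAP*

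**What the plan says.** SAP 4.9.2 introduces a list of exposure parameters: "For each study medication (PEGPH20 and pembrolizumab), exposure will be summarized using descriptive statistics by cancer type and in total". One item in that list is dose delay: "A treatment cycle is considered delayed if the first dose date of the following cycle is greater than 28 days", counted "after the first dose date of the cycle of interest". The sentence names no drug.

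On schedule, Protocol 8.3 states: "PEGPH20 will be administered on Day 1, Day 8 and Day 15 of each 21-day cycle". Pembrolizumab is given once per cycle, on Day 1. SAP 3.1.2, in line with Protocol 8.3, adds: "If a dose of PEGPH20 is missed on Day 1 of Cycle 2 or beyond, the cycle will continue as scheduled". The note under Table 6 in Protocol 8.3.1.3 adds: "If PEGPH20 is held on Day 1 of treatment cycles 2+, pembrolizumab must still be given". Both documents also say that when pembrolizumab itself is held, the cycle does not begin until it is given.

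The dose-intensity part of SAP 4.9.2 allows for a late first PEGPH20 dose: "if the day of the visit of first dose date of last cycle is not 1, then an adjustment should be made", by subtracting 7 days for Day 8 or 14 days for Day 15. That adjustment is given only for the end date of the last cycle. The delay rule has none.

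**The concern.** A missed PEGPH20 Day 1 dose is an omission within an on-time cycle. A delayed cycle is a different event: the whole cycle starts late. The delay rule can confuse the two for PEGPH20, because the first PEGPH20 dose date of a cycle need not be the date on which the cycle started. A late first dose in the following cycle lengthens the measured gap. A late first dose in the index cycle shortens it.

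What is at stake is the PEGPH20 count of subjects with at least one delay and of cycles with a delay. These sit in the descriptive tolerability evidence of an open-label, non-randomized study. The circumstances that produce the error are foreseeable. For Grade 3 non-musculoskeletal, non-thromboembolic events potentially related to PEGPH20, Table 6 holds the drug and provides for resumption if the event improves within 14 days. Such a hold beginning on Day 1 can end at Day 15 of the same cycle. The PEGPH20 and pembrolizumab delay rows would then not measure the same thing, since pembrolizumab has one dose per cycle and no such problem.

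**Working it through.** **Inputs**
- Cycle length 21 days; PEGPH20 on Days 1, 8 and 15 (Protocol 8.3).
- Flag: gap strictly greater than 28 days (SAP 4.9.2).
- Visit window ±2 days (Protocol 8).
- A missed PEGPH20 Day 1 dose leaves the cycle on schedule (SAP 3.1.2, Protocol 8.3).

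**Formula.** Let *d* be the true delay of the next cycle's start, in days. Let the offset be 0, 7 or 14 for a first PEGPH20 dose on Day 1, 8 or 15.

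Gap = 21 + *d* + offset(next cycle) − offset(index cycle)

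**Benchmark.** With Day 1 starts in both cycles the gap is 21 + *d*. It exceeds 28 when *d* is at least 8, so in effect the rule flags cycles more than 7 days late.

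**All nine combinations**

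| First PEGPH20 dose, index cycle | First PEGPH20 dose, next cycle | Gap if on time | Flagged if on time? | Smallest true delay flagged |
|---|---|---|---|---|
| Day 1 | Day 1 | 21 | no | 8 |
| Day 1 | Day 8 | 28 | no (not above 28) | 1 |
| Day 1 | Day 15 | 35 | yes | already flagged on time |
| Day 8 | Day 1 | 14 | no | 15 |
| Day 8 | Day 8 | 21 | no | 8 |
| Day 8 | Day 15 | 28 | no (not above 28) | 1 |
| Day 15 | Day 1 | 7 | no | 22 |
| Day 15 | Day 8 | 14 | no | 15 |
| Day 15 | Day 15 | 21 | no | 8 |

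**False delays after a Day 1 start**
- First dose on Day 15 (Days 1 and 8 both omitted): 21 + 14 = 35 days. With each visit free to move ±2 days the range is 31-39, so it is always flagged.
- First dose on Day 8 (only Day 1 omitted): 21 + 7 = 28 days, not flagged on the nominal schedule. With windows the range is 24-32, and it is flagged when drift lengthens the gap by at least 1 day. If all 25 combinations of the two visit shifts were equally likely (an assumption, not a document figure), 10 of 25, or 40%, would be flagged.

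**Uncounted delays when the next cycle starts on Day 1**
- Index cycle began on Day 8: gap = 14 + *d*, flagged only from *d* = 15. Delays of 8-14 days are not counted.
- Index cycle began on Day 15: gap = 7 + *d*, flagged only from *d* = 22. Delays of 8-21 days are not counted. The top of this range reaches the 21-day delay that Protocol 7.3.1 lists among possible reasons for stopping treatment.

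**Check of the remedy.** Removing the offsets from both dates gives an on-time gap of 21 days in all nine combinations. None is flagged, and the smallest true delay flagged is 8 days throughout.

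**The case against.** The strongest counter-argument is that the drug-specific reading is an inference. The delay sentence speaks of a treatment cycle and names no drug. If its dates mean the first dose of either drug, Day 1 pembrolizumab would anchor the cycle and the problem would largely disappear. That reading is possible but has less support. The item sits in the per-drug list, the same section refers expressly to either medication when it defines overall treatment duration, and its dose-intensity rule expects a PEGPH20 first dose on Day 8 or 15. On either reading the SAP should say which date is meant.

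A reader might infer that every omitted Day 1 dose in an on-time cycle is counted as a delay. The documents do not support that: omitting Day 1 alone gives exactly 28 days on the nominal schedule, and the rule requires more than 28.

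A reader might also infer that real delays are lost to the study. They are not. A cycle start moves back when pembrolizumab is held, and the same rule in the pembrolizumab rows would still show it. Within the PEGPH20 row, delays of 15 or 22 days and more are still flagged.

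Nor are omissions double counted in any total. Omission and delay are separate descriptive rows that nothing adds together.

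Finally, dose intensity already carries the Day 8/15 adjustment, and safety analyses involve no inferential tests. This limits the importance of the point but does not make the delay rule correct.

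**Conclusion.** The error is real but minor. Read per drug, which is the better-supported reading, the rule's effective threshold for PEGPH20 moves by 7 or 14 days whenever the two cycles being compared began PEGPH20 on different days. It can flag an on-time cycle and miss a true delay of 8-14 or 8-21 days under the conditions set out above.

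The effect is confined to the descriptive PEGPH20 delay counts. Response, DLT, MTD, RP2D and adverse-event analyses are untouched, as are the power calculations. The documents do not say how often a cycle would begin PEGPH20 on Day 8 or 15, so the number of misclassified cycles cannot be estimated. The conclusion rests on the drug-specific reading of the first dose date and on cycles otherwise keeping to the 21-day schedule.

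**What to change.** In SAP 4.9.2, define cycle delay for both drugs from the Day 1 visit date (the pembrolizumab dose date) of one cycle to that of the next. PEGPH20 doses missed on Day 1 then count only as omissions. This definition also covers a cycle in which no PEGPH20 is given, where a PEGPH20-based anchor is undefined.

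If the PEGPH20 dose date is kept as the anchor, subtract 7 or 14 days from either date when that cycle's first PEGPH20 dose was on Day 8 or Day 15, as the section already does for the last cycle. This is only an approximation within the ±2-day windows, because the adjusted date need not equal the actual Day 1 visit date.

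Changing the 28-day cut-off would not help, since the offset term remains at any cut-off. The cost is one SAP sentence and minor programming, with no new data.
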